5.3.4 Handling of Withdrawals

The primary reason for withdrawal from the study will be recorded on the Study Status data collection form. Parents/guardians will be encouraged to complete the Early Termination Visit, as listed in Section 7.5. Unless they expressly state that they wish to have no additional follow-up or data collection, subjects who withdraw from the study will receive a follow-up phone call approximately one week after their withdrawal. This will allow the site to assess the status of the subject and determine if any medical follow up care was sought. Although subjects are free to withdraw at any time or may be withdrawn by the site PI or appropriate sub-investigator at any time, subjects will be encouraged to remain in this study for follow-up assessments (may be by telephone rather than in person) continuing through approximately 1 month after study treatment.

Every attempt will be made to follow all ongoing solicited events or serious adverse events, as well as new-onset chronic medical conditions, to resolution or until the subject's condition becomes stable.

Subjects who discontinue treatment will be followed according to the study protocol and will not be replaced.

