6.3.2. Complete Case (CC) Cohorts

Subjects in a CC analysis are analyzed as randomized but excluded from analysis if missing data prevents assigning an unambiguous value to the DOOR endpoint or if the subject has not received at least one dose of study product. The CC-V1 cohort will consist of all subjects with sufficient data to define unambiguously the Outcome Assessment Visit #1 DOOR. The CC-V2 cohort will consist of all subjects with sufficient data to define unambiguously the Outcome Assessment Visit #2 DOOR.

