6.5. Missing Data

While all efforts will be made to minimize missing data, some missing data is expected. Whenever possible, subjects terminating from the study early will be given an early termination visit during which the available components of the DOOR and related measures can be recorded. The primary analysis will use multiple imputation with linear models to impute values using available information (treatment, randomization strata variables, and available visit information), assuming a missing at random (MAR) model. Secondary analyses will further examine the robustness of this analysis, including a “worst case analysis” in which all imputations of missing

data will be the worst case (result in the lowest possible DOOR given available information) for subjects in the 5-day arm and best case for subjects in the 10-day arm. Day 1 in this study is defined as the date of first receipt of study product. If a subject has no record of study product administration or did not receive a first dose of study product, but has other post-randomization data, Day 1 will be imputed as the date 5 days after the date of first receipt of initial antibiotic.

In some cases, a subject may have DOOR defined despite missing some of its components, in which case the subject will be eligible for inclusion into the CC and ATP analysis populations. In analyses of the components of the DOOR using the CC and ATP analysis populations, data will be analyzed as available and missing data will not be imputed.

The study includes several composite variables with rules for assignment, missingness, and imputation described below.

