6.5.3. Resolution of Symptoms at OAV#1 or OAV#2

Resolution of symptoms is defined as the absence of all of the following:

- Fever at the OAV, as defined above
- Elevated respiratory rate (RR >50 breaths/minute for children <24 months of age and >40 breaths/minute for children 24-71 months of age) at the time of the Outcome Assessment Visit (VS1.RESPB);
- Presence of cough grade 2 or 3 at the Outcome Assessment Visit (ACRCGHSV)

If the subject died at any point of participation in the study, then the subject will be analyzed as not having resolution of symptoms at either Outcome Assessment Visit. Otherwise, if the subject did not have adequate clinical response at OAV#1 or OAV#2, then the subject will be analyzed as not having resolution of symptoms at the respective Outcome Assessment Visit(s). Otherwise, if fever, elevated respiratory rate, or presence of grade 2 or 3 cough is indicated at OAV#1 or OAV#2, then the subject does not have resolution of symptoms at the respective Outcome Assessment Visit (regardless of whether some components of the resolution of symptoms are missing). Otherwise, if fever, respiratory rate, and presence of cough are all non-missing and are indicated as 'No' at OAV#1 or OAV#2, then the subject has resolution of symptoms at the respective Outcome Assessment Visit. Otherwise, resolution of symptoms is missing at the Outcome Assessment Visit.

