6.5.4. Most Severe Solicited Event at OAV#1 and OAV#2

The maximum severity at OAV #1 will be calculated based on the following rules:

- If a subject has missing data for the severity grade of any solicited event for two consecutive days or has missing data for more than two days from Day 1 to Day 5 then the most severe solicited event at OAV#1 will be missing.
- Otherwise if a subject has missing data for one or two non-consecutive days from Day 1 to Day 5 then the missing severity will be imputed as the maximum severity grade taken across the previous day and the day after the day with a missing severity. As a special case, for subjects missing severity for Day 1, the missing severity will be imputed as the Severity from Day 2. For subjects missing severity at Day 5 but not missing severity at Day 6, the missing severity will be imputed as the maximum of severity gradings from Day 4 and Day 6. For these subjects with severity grades (0 to 3) recorded or imputed for every solicited event (irritability, vomiting, diarrhea, allergic reaction, stomatitis, and candidiasis) from Day 1 to Day 5, inclusive, the most severe solicited event at OAV#1

will be the maximum severity grade taken across all solicited events from Day 1 to Day 5.

- If a subject had any solicited event of severity grade 3 from Day 1 to Day 5, then the most severe solicited event at OAV#1 will be grade 3, regardless of the presence of missing data during that period.

In a similar manner, the maximum severity at OAV #2 will be calculated based on the following rules:

- If a subject has missing data for the severity grade of any solicited event for more than three consecutive days or has missing data for more than five days from Day 1 to Day 18 then the most severe solicited event at OAV#2 will be missing.

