6.5.5. Ordinal Clinical Response at OAV#1 or OAV#2

If the subject died at any point of study participation, then OCR at OAV#1 will be 8.

Else if the subject has missing ACR at OAV#1 then OCR at OAV#1 will be missing.

Else if the subject did not have ACR at OAV#1 and was hospitalized from Day 1 to Day 5 then OCR at OAV#1 will be 7.

Else if the subject did not have ACR at OAV#1 and was not hospitalized from Day 1 to Day 5 then OCR at OAV#1 will be 6.

Else if the subject has missing resolution of symptoms at OAV#1 then OCR at OAV#1 will be missing.

Else if the subject did not have resolution of symptoms at OAV#1 then OCR at OAV#1 will be 5.

Else if the subject has missing most severe solicited event at OAV#1 then OCR at OAV#1 will be missing.

Else if the subject had a most severe solicited event of grade 3 at OAV#1 then OCR at OAV#1 will be 4.

Else if the subject had a most severe solicited event of grade 2 at OAV#1 then OCR at OAV#1 will be 3.

Else if the subject had a most severe solicited event of grade 1 at OAV#1 then OCR at OAV#1 will be 2.

Else OCR at OAV#1 will be 1.

If the subject died at any point of study participation, then OCR at OAV#2 will be 8.

Else if the subject has missing ACR at OAV#2 then OCR at OAV#2 will be missing.

Else if the subject did not have ACR at OAV#2 and was hospitalized from Day 1 to Day 18 then OCR at OAV#2 will be 7.

Else if the subject did not have ACR at OAV#2 and was not hospitalized from Day 1 to Day 18 then OCR at OAV#2 will be 6.

Else if the subject has missing resolution of symptoms at OAV#2 then OCR at OAV#2 will be missing.

Else if the subject did not have resolution of symptoms at OAV#2 then OCR at OAV#2 will be 5.

Else if the subject has missing most severe solicited event at OAV#2 then OCR at OAV#2 will be missing.

Else if the subject had a most severe solicited event of grade 3 at OAV#2 then OCR at OAV#2 will be 4.

Else if the subject had a most severe solicited event of grade 2 at OAV#2 then OCR at OAV#2 will be 3.

Else if the subject had a most severe solicited event of grade 1 at OAV#2 then OCR at OAV#2 will be 2.

Else OCR at OAV#2 will be 1.

Note that in some cases OCR can be defined even if some components are missing. For instance, if a subject had record of receipt of study product and did not have adequate clinical response at OAV#1, OCR at OAV#1 would still be defined even if most severe solicited event at OAV#1 was missing.

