8.2.5. Adequate Clinical Response at Outcomes Assessment Visits #1 and #2

Separately for Outcome Assessment Visit #1 and #2, using CC cohorts, a forest plot of 95% confidence intervals for the risk difference of adequate clinical response as well as the following interventions for persistent or worsening pneumonia: (1) ED/clinic visits, (2) hospitalizations, (3) surgical procedures, and (4) non-study systemic antibiotics will be given (Figure 11 and Figure 13). Results will also be reported in tables (Table 26 and Table 28), and tests for differences in proportions between treatment arms will be given by Fisher's exact tests. The Newcombe method with continuity correction will be used to compute all 95% confidence intervals for risk differences.

Separately for Outcome Assessment Visit #1 and #2, using CC cohorts, a forest plot of 95% confidence intervals for the risk difference of the following interventions for any reason: (1) ED/clinic visits, (2) hospitalizations, (3) surgical procedures, and (4) non-study systemic antibiotics will be given (Figure 12 and Figure 14). Results will also be reported in tables (Table 27 and Table 29), and tests for differences in proportions between treatment arms will be given by Fisher's exact tests. The Newcombe method with continuity correction will be used to compute all 95% confidence intervals for risk differences.

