Elevated respiratory rate ³									
Cough ⁴									

Note: N=X indicates the number of subjects in the CC-V1 analysis population and the respective treatment group with complete records of fever, elevated respiratory rate, and cough at Outcome Assessment Visit #1.

¹ P-value obtained by Fisher Exact Test.

² As defined in Section 6.5.2 of the SAP.

³ Elevated respiratory rate (RR >50 breaths/minute for children <24 months of age and >40 breaths/minute for children 24-71 months of age) at the time of the Outcome Assessment Visit.

⁴ Presence of cough Grade 2 or 3 at the Outcome Assessment Visit.

Table 25: Lack of Resolution of Symptoms and Its Components at Outcome Assessment Visit #2 (CC-V2 Cohort) by Treatment Group

Event	Standard Course (N=X)			Short Course (N=X)			Difference in Proportion		P-value ¹
	n	%	95% CI	n	%	95% CI	%	95% CI	
Lack of Resolution of Symptoms									
Fever ²									
Elevated respiratory rate ³									
Cough ⁴									

Note: N=X indicates the number of subjects in the CC-V2 analysis population and the respective treatment group with complete records of fever, elevated respiratory rate, and cough at Outcome Assessment Visit #2.

¹ P-value obtained by Fisher Exact Test.

² As defined in Section 6.5.2 of the SAP.

³ Elevated respiratory rate (RR >50 breaths/minute for children <24 months of age and >40 breaths/minute for children 24-71 months of age) at the time of the Outcome Assessment Visit.

⁴ Presence of cough Grade 2 or 3 at the Outcome Assessment Visit.

Table 26: Risk of Lack of Adequate Clinical Response and Its Components from Day 1 to Day 5 (CC-V1 Cohort) by Treatment Group

Event	Standard Course (N=X)			Short Course (N=X)			Difference in Proportion		P-value ¹
	n	%	95% CI	n	%	95% CI	%	95% CI	
Lack of Adequate Clinical Response									
ED or Clinic Visit ²									
Hospitalization ²									
Surgical Procedure ³									
Receipt of Non-Study Antibiotic ⁴									

Note: N=X indicates the number of subjects in the CC-V1 analysis population.

¹ P-value obtained by Fisher Exact Test.

² For persistent or worsening pneumonia that occurs after randomization and receipt of at least one dose of study drug.

³ For pneumonia or treatment for a complication of pneumonia, including but not limited to drainage of pleural fluid, placement of a chest tube, video assisted thoracoscopic surgery, or thoracotomy procedures.

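### The final comparison of adequate clinical response uses complete-case cohorts whose membership depends partly on that response, which modestly inflates failure rates among treated children whose response is known

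*SAP*

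**What the plan says.** **The comparison.** SAP 8.2.5 calls for, by visit and "using CC cohorts, a forest plot of 95% confidence intervals for the risk difference of adequate clinical response", plus visits, hospitalizations, surgery and non-study antibiotics, with Fisher's exact tests (Tables 26-29, Figures 11-14). Protocol 11.4.2 prespecifies the same cohorts. The Table 26 note fixes the denominator: "N=X indicates the number of subjects in the CC-V1 analysis population".

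**Who is in the cohort.** Under SAP 6.3.2 a child is "excluded from analysis if missing data prevents assigning an unambiguous value to the DOOR endpoint", or if no dose was taken. SAP 6.5 adds that "a subject may have DOOR defined despite missing some of its components", and that such a child is eligible for the CC set.

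**Failures.** SAP 6.5.5 assigns rank 6 or 7 before it looks at symptoms or solicited events. Its closing note says that for such a child "OCR at OAV#1 would still be defined even if most severe solicited event at OAV#1 was missing". SAP 6.5.3 closes the other gap: "if the subject did not have adequate clinical response at OAV#1 or OAV#2, then the subject will be analyzed as not having resolution of symptoms".

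**Successes.** Under SAP 6.5.5 a child with ACR also needs a known resolution status and, if symptoms resolved, a known worst solicited event. Otherwise the ordinal clinical response (OCR), and with it DOOR, is missing. At the first visit the worst event is missing after "missing data for the severity grade of any solicited event for two consecutive days", or after more than two missing days in Days 1-5, unless a grade 3 event was recorded. At the second visit the limits are more than three consecutive days or more than five days in Days 1-18.

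**Where gaps may come from.** Protocol 5.3.4 says of children who withdraw that "subjects will be encouraged to remain in this study for follow-up assessments (may be by telephone rather than in person"). SAP 6.3 lists a visit not held in person as a reason for exclusion from the according-to-protocol cohorts, but not from CC.

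**The concern.** Take two treated children who both have the visit, and whose ACR is therefore known under SAP 6.5.1. Both lack a respiratory rate because the visit was by telephone, or both left the diary blank for two consecutive days. The child who failed stays in CC. The child who did well, with no fever or grade 2-3 cough and no grade 3 event, leaves. The table that reports failure thus discards observed successes but keeps matching failures.

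This matters because ACR is the component that shows whether a favourable DOOR hides more clinical failures. The footnote to the Table 14 shell itself says a DOOR result has to be read together with its components. The interim report (SAP 6.6) already uses a better population for the same plot: treated children who completed the first visit. The final plan narrows this without giving a reason.

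**Working it through.** **1. The plan's own figures.** The documents give no expected failure rate, power or sample size for the ACR comparison. The primary sample size reproduces: Noether's formula gives (1.960 + 1.282)² / (12 × 0.25 × 0.10²) = 350.2, against a stated 360. The relevant planning figure is the 90% evaluable assumption in SAP Section 5: 0.90 × 400 = 360.

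**2. Outcome by type of gap (visit held, at least one dose).**

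| Gap | ACR = no | ACR = yes |
|---|---|---|
| Respiratory rate missing | Resolution set to no, rank 6 or 7, kept | Dropped, unless fever or grade 2-3 cough was observed (rank 5) |
| Diary gap beyond 6.5.4 limits | Rank 6 or 7, kept | Dropped if symptoms resolved, unless a grade 3 event was recorded |
| Smaller diary gap | Kept | Filled in, kept |

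**3. Size.** Let f be the true failure rate among treated children with known ACR, and d the share of successes *actually dropped* (not the share with any gap). Both are assumptions. The CC failure rate is

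f / [f + (1 − f)(1 − d)].

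- f = 5%, d = 5%: 0.05 / (0.05 + 0.95 × 0.95) = 0.05 / 0.9525 = 5.25%.
- f = 5%, d = 10%: 0.05 / (0.05 + 0.95 × 0.90) = 0.05 / 0.905 = 5.52%. With 200 per arm, 10 failures and 190 successes become 10 and 171, and 10/181 = 5.52%.
- f = 1%: 1.05% and 1.11%. f = 10%: 10.47% and 10.99%.

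The relative inflation cannot exceed 1/(1 − d), which is 1.11 at d = 10%.

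**4. Risk difference.**
- Equal f and equal d: zero bias.
- Equal f = 5%, d = 10% in one arm and 5% in the other: 5.52 − 5.25 = about 0.3 points.
- True rates 10% and 5%, d = 10% in both: 10.99 − 5.52 = about 5.5 points, against a true 5.0.

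**5. Check by simulating the SAP rules.** Assumed inputs were 5% failure, 5% respiratory-rate gaps, 5% disqualifying diary gaps, 8% persistent cough and 5% grade 3 events. The true rate was 5.03%. The CC rate was 5.48%, with 8.3% of children dropped. Excluding every child with a gap regardless of outcome gave 5.03%, so the inflation comes from the outcome-dependent rule and not from missingness as such.

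**6. Alternative reading of the diary rule.** The CC exclusion list in SAP 6.3 and the Table 5 shell name missing solicited-event severity with no exception for failures. Read literally, that would also drop failures with a diary gap. The same simulation then gives 5.22% against 5.03%: smaller, but not zero, because the respiratory-rate route remains.

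**The case against.** Several points on the other side have force.

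- **Failure can be seen elsewhere.** A reader might infer that the plan shows ACR nowhere outside CC. It does not support that. Table 57 gives pneumonia-related visits and treatments by arm, in a section that uses the safety population. The ITT and worst-case cumulative difference plots include OCR of 5 or less versus more, which is the ACR split. The interim plot uses treated children who completed the first visit. These views are respectively descriptive, dependent on imputed OCR, and interim, so none replaces the final named comparison.
- **Not every gap causes exclusion.** It is tempting to count all successes with missing diary or respiratory-rate data as lost. The table in the working shows they are not, so d must be the share actually dropped.
- **Large scenarios do not fit the plan.** Dropping 20% of successes in one arm and 5% in the other would give about 0.9 points. That averages 12.5% of successes, or 0.125 × 0.95 = 11.9% of children, which exceeds the plan's whole 10% non-evaluable allowance. That allowance must also cover missed visits. Families are blinded to a matched placebo, and nothing in the documents points to gaps that differ by arm.
- **The bias is small beside sampling error.** With 180 per arm at 5%, the 95% half-width is 1.96 × √(2 × 0.05 × 0.95 / 180) = 4.5 points.
- **Direction.** A reader might infer that failure rates are inflated in absolute terms. Under SAP 6.5.1 a surviving child who misses the visit has ACR set to missing even if a failure is known, so failures are lost by that route too.

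What remains is that known outcomes are discarded by a rule that depends on the outcome, in a secondary comparison that needs no such rule.

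**Conclusion.** The point holds in limited form. The final ACR comparison uses a cohort selected partly on ACR, and relative to treated children with known ACR this modestly raises the failure rate: from an assumed 5% to 5.25% or 5.52% when 5% or 10% of successes are dropped. The risk difference shifts by about 0.3 points when dropping is 10% versus 5%, and a true 5.0-point difference reads about 5.5 when 10% are dropped in both arms. With equal true rates and equal dropping it is unbiased. The failure and dropping rates are assumptions; for the earlier trial that it cites, the plan reports no failures at 5 or 10 days. Missed visits are a separate issue. The respiratory-rate route holds on any reading of the SAP, whereas the diary route rests on 6.5 and 6.5.5 taking precedence over the list in 6.3.

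**What to change.** In SAP 8.2.5, Tables 26-29 and Figures 11-14, analyse ACR and the interventions in all randomized children who received at least one dose and have non-missing ACR at that visit under 6.5.1, as randomized, whether or not DOOR is complete. Keep the prespecified CC result as an accompanying row. The CC cohorts for DOOR itself need not change.

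Reconcile the CC exclusion list in SAP 6.3 and the Table 5 shell with 6.5 and 6.5.5, so that it is clear whether a failure with a diary gap stays in CC.

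Protocol 11.4.2 prespecifies the CC cohorts, and SAP Section 13 states that the planned analyses are unchanged. Either the protocol has to be aligned or the change recorded and justified in Section 13.

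The cost is that documentation, plus ACR denominators that differ slightly from those of the CC DOOR analyses. No new data are needed. The change does not recover children who miss the visit.

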8.2.6. Ordinal Clinical Response at Outcomes Assessment Visits #1 and #2

Analysis of the ordinal clinical response (OCR) at Outcome Assessment Visits #1 and #2. Separately for OCR at each of the two visits, a first ITT analysis (superiority/inferiority) will test the null hypothesis that

$$\Pr(\text{OCR is better in short course}) + 0.5 \Pr(\text{OCR is equal}) = 0.5.$$

A second ITT analysis (non-inferiority) will test the null hypothesis that

$$\Pr(\text{OCR is better in short course}) + 0.5 \Pr(\text{OCR is equal}) < 0.4.$$

ITT, CC, ATP, and worst case analyses will plot cumulative difference plots and test whether the overall distributions of OCR are equivalent between the treatment arms for OCR at each of the two visits.

Cumulative difference plots (Figure 15, Figure 16, Figure 17, Figure 18 and Figure 19, Figure 20, Figure 21, Figure 22) are produced as follows. For $i \in \{1,2,3,4,5,6,7\}$, the difference in proportions of subjects with $\text{OCR} \leq i$ between treatment arms is plotted (i on x-axis and

difference in proportion on y-axis), together with 95% confidence intervals computed using the Newcombe method with continuity correction.

For CC-V1, CC-V2, ATP-V1, and ATP-V2 analysis populations, OCRs will be summarized by treatment group and tests of overall distributions of OCR will be performed using the mean score statistic (QS). The mean score statistic is obtained from PROC FREQ in SAS using the “chisq” option and is denoted in output as the “Mantel-Haenszel Chi-Square” statistic.

8.2.6.1. ITT Analyses of OCR at Outcomes Assessment Visit #1

Twenty (20) multiple imputation datasets for OCR at Outcome Assessment Visit #1 will be generated in manner analogous to that described in Section 8.1.1, except using OCR at Outcome Assessment Visit #1 in place of DOOR at Outcome Assessment Visit #1 for the response. Also, analogous to Section 8.1.1, the Mann-Whitney U statistic will be computed for each of the datasets and combined using Rubin’s Rules to generate the test statistic W and a p-value for the test of the null hypothesis that

$$\Pr(\text{OCR at Outcome Assessment Visit \#1 is better in short course}) + 0.5 \Pr(\text{OCR at Outcome Assessment Visit \#1 is equal}) = 0.5.$$

The F-test using the W statistic will be inverted to produce a 95% confidence interval for $\Pr(\text{OCR is better in short course}) + 0.5 \Pr(\text{OCR is equal})$. Whether the lower bound of this confidence interval is greater than 0.4 will serve as a test of the non-inferiority null hypothesis that

$$\Pr(\text{OCR at Outcome Assessment Visit \#1 is better in short course}) + 0.5 \Pr(\text{OCR at Outcome Assessment Visit \#1 is equal}) < 0.40.$$

Results will be reported in [Table 30](#).

